8.3.9 Adverse Events

AEs will be coded using the MedDRA coding dictionary. Only TEAEs will be included in summary tables, while non-TEAEs will be listed separately.

The number and percentage of subjects reporting TEAEs will be tabulated by treatment arm as well as the total number of TEAEs. Summaries will be presented by SOC and PT, and further by severity and relationship to study drug. If a subject has more than one event per PT, the subject will be only counted once and in addition the number of events will also be shown. The calculation of percentages will be based on the number of subjects within each treatment arm in SAF population.

The relationship will be classified as "related" and "not related" for TEAEs. Serious AEs will be separately listed. When summarizing TEAEs by severity and relationship, each subject will be counted once within a SOC or a PT by using the event with the highest severity and greatest relationship within each classification.

The following summaries will be presented:

Overview of treatment emergent adverse events by the following categories:

Protocol title: A RANDOMIZED, VEHICLE-CONTROLLED, SAFETY AND EFFICACY STUDY OF EVO101 IN ADULT SUBJECTS WITH ATOPIC DERMATITIS

Sponsor code: EVO101-AD001

code: EPQ1001

Version number: Final 1.0

Date: 17-AUG-2023

- TEAEs
- Serious TEAEs
- Related TEAEs
- Serious related TEAEs
- TEAEs with CTCAE grade ≥ 3
- TEAEs leading to study drug withdrawal
- TEAEs leading to death
- TEAEs by SOC and PT
- TEAEs by PT
- TEAEs by intensity (CTCAE grade: 1, 2, 3, 4 or 5), SOC and PT
- Serious TEAEs by SOC and PT
- Related TEAEs by SOC and PT
- Serious related TEAEs by SOC and PT
- TEAEs leading to study drug withdrawal by SOC and PT
- TEAEs leading to death by SOC and PT
- Local skin reactions TEAEs by SOC and PT

Additionally, two listings will be created for all AEs and serious AEs including the SOC, PT, reported term, start/end date, relative start/end date, AE duration, seriousness, intensity, relationship with the study drug, action taken with the study drug, outcome, application site flag and treatment-emergent flag.

8.3.10 Other Safety Assessments

All the analyses described below will be presented by treatment group and will be based on the SAF population. Percentages will be based on the available data within each treatment arm except for the shift table for which percentages will be based on the total number of subjects in each treatment arm.

Protocol title: A RANDOMIZED, VEHICLE-CONTROLLED, SAFETY AND EFFICACY STUDY OF EVO101 IN ADULT SUBJECTS WITH ATOPIC DERMATITIS

Sponsor code: EVO101-AD001

code: EPQ1001

Version number: Final 1.0

Date: 17-AUG-2023

Vital Signs

For all vital signs parameters [systolic and diastolic blood pressure (mmHg), pulse rate (beats/min), respiratory rate (breaths/min), temperature (°F)] summary statistics will be provided at the following visits: Baseline, Week 2, Week 4 and Week 8. Additionally, Weight will be provided at baseline and Week 8.

For these parameters, the following summaries will be provided at each time-point:

- A summary table showing the values and the changes from baseline
- A summary table showing the number and percentage of subjects reporting "normal", "abnormal, not clinically significant" and "abnormal, clinically significant" results
- A shift table presenting the number and the percentage of subjects in each bivariate category (baseline versus each post-baseline visit)
- Listing by subject including the parameter, visit, date of the assessment, the value, change from baseline and Normal/abnormal classification.

Clinical Laboratory Measurements

Analysis of clinical laboratory data will be performed for Hematology, Biochemistry and Urinalysis tests at the following visits: Baseline and Week 8.

The following laboratory tests will be summarized:

- Hematology: hematocrit, hemoglobin, red blood cells (RBC) count, white blood cells (WBC), percentage of Neutrophils, Lymphocytes, Monocytes, Eosinophils and Basophils, Mean Corpuscular Hemoglobin (MCH), Mean Corpuscular Hemoglobin Concentration (MCHC), Mean Corpuscular Volume (MCV), RBC morphology, Platelet count and Absolute of Neutrophils, Lymphocytes, Monocytes, Eosinophils and Basophils.
- Clinical chemistry: sodium, potassium, chloride, calcium, phosphorus, bicarbonate, uric acid, blood urea nitrogen, creatinine, total protein, albumin, total and direct bilirubin, Aspartate aminotransferase (AST), Alanine aminotransferase (ALT), Alkaline phosphatase (ALP) and non-fasting Glucose.
- Urinalysis: pH, specific gravity, protein, glucose, ketones, bilirubin, blood, nitrite, leukocytes esterase, microscopic examination and urobilinogen.

For those parameters, the following summaries will be provided at each time-point:

- A summary table showing the values and the changes from baseline
- A summary table showing the number and percentage of subjects reporting "normal", "abnormal, not clinically significant" and "abnormal, clinically significant" results

Protocol title: A RANDOMIZED, VEHICLE-CONTROLLED, SAFETY AND EFFICACY STUDY OF EVO101 IN ADULT SUBJECTS WITH ATOPIC DERMATITIS

Sponsor code: EVO101-AD001

code: EPQ1001

Version number: Final 1.0

Date: 17-AUG-2023

- A shift table presenting the number and the percentage of subjects in each bivariate category (baseline versus each post-baseline visit)
- 3 listings (hematology, chemistry and urinalysis) by subject including the parameter, visit, date of the assessment, value, change form baseline and Normal/abnormal classification.

Cardiac Assessments

For all ECG parameters [ECG Mean Heart Rate (beats/min), RR interval (msec), PR interval (msec), QRS duration (msec), QT interval (msec), QTcB interval (msec) and QTcF interval (msec)] summary statistics will be given at the following visits: Baseline and Week 8.

For those parameters, the following summaries will be provided at each time-point:

- A summary table showing the values and the changes from baseline.
- A summary table showing the number and percentage of subjects reporting "normal", "abnormal, not clinically significant" and "abnormal, clinically significant" results for the overall interpretation.
- A shift table presenting the number and the percentage of subjects in each bivariate category (baseline versus each post-baseline visit) for the overall interpretation.
- Listing by subject including the parameter, visit, date of the assessment, the value, change from baseline, Normal/abnormal classification and any comments reported related to the result.

Physical Examination

For all body systems (general appearance, dermatological other than Atopic Dermatitis, head, ears, eyes, nose, throat, respiratory, cardiovascular, abdominal, neurological, musculoskeletal and lymphatic body system) collected in the physical examination)] summary statistics will be given at the following visits: Baseline and Week 8.

For those parameters, the following summaries will be provided at each time-point:

- A summary table showing the number and percentage of subjects reporting "normal", "abnormal, not clinically significant" and "abnormal, clinically significant" results for the overall interpretation.
- A shift table presenting the number and the percentage of subjects in each bivariate category (baseline versus each post-baseline visit) for the overall interpretation.
- Listing by subject including the parameter, visit, date of the assessment, the value, change from baseline, Normal/abnormal classification and any comments reported related to the result.

COVID-19 and pregnancy tests

Statistical Analysis Plan Protocol title: A RANDOMIZED, VEHICLE-CONTROLLED, SAFETY AND EFFICACY STUDY OF EVO101 IN ADULT SUBJECTS WITH ATOPIC DERMATITIS Sponsor code: EVO101-AD001 code: EPQ1001 Version number: Final 1.0 Date: 17-AUG-2023

Listing by subject including the test, visit, date of the assessment and the result will be provided for Covid-19 and pregnancy tests.

8.4 Level of Significance, Multiple Comparisons and Multiplicity

For secondary efficacy endpoints, no adjustments for multiplicity will be applied.

8.5 Multicenter Studies

Not applicable.

8.6 Adjustment for Covariates

Covariates used for adjustment in the efficacy models are specified in the corresponding efficacy sections (8.3.5, 8.3.6).

8.7 Examination of Subgroups

Not applicable.

8.9 Interim Analysis

No Interim analysis is planned for this study.

8.10 Data Monitoring Committee

No data monitoring is planned for this study.

8.11 References

Not applicable.

Protocol title: A RANDOMIZED, VEHICLE-CONTROLLED, SAFETY AND EFFICACY STUDY OF EVO101 IN ADULT SUBJECTS WITH ATOPIC DERMATITIS

Sponsor code: EVO101-AD001

code: EPQ1001

Version number: Final 1.0

Date: 17-AUG-2023

9 Tables, Listings and Figures Overview

The tables, figures and listing derived from the analyses described in this SAP will be allocated and numbered according to the ICH-E3 guidelines. The tables and figures will be displayed in 3 sections from section 14 of the CSR:

14.1 DISPOSITION, ANALYSIS POPULATIONS, BASELINE AND DISEASE HISTORY

14.2 EFFICACY DATA

14.3 SAFETY DATA

The listing will be part of the appendix 16 of the CSR.

9.1 Tables to be Produced for the Clinical Study Report

		Key/Top Line
Title	Population	Results
14.1.1.1 Study disposition and discontinuation and reasons for withdrawal	ITT	Х
14.1.1.2 Analysis sets and primary reason for exclusion	ITT	Х
14.1.1.3 Screen failures and reasons	All	
14.1.2.1 Major protocol deviations	ITT	
14.1.3.1 Demographic characteristics	ITT	Х
14.1.4.1 Medical/Surgical history	ITT	
14.1.5.1 Prior medications	SAF	
14.1.5.2 Concomitant medications	SAF	
		_
		┛

Protocol title: A RANDOMIZED, VEHICLE-CONTROLLED, SAFETY AND EFFICACY STUDY OF EVO101 IN ADULT SUBJECTS WITH ATOPIC DERMATITIS

Sponsor code: EVO101-AD001

code: EPQ1001

Version number: Final 1.0

Date: 17-AUG-2023

		_
		₽
14.2.3.1 Pharmacokinetics: Absolute values by visit	PK	
14.3.1.1 Summary of Treatment Emergent Adverse Events	SAF	Х
14.3.1.2 Treatment Emergent Adverse Events by System Organ Class and	0.45	×
Preferred Term	SAF	X
14.3.1.3 Treatment Emergent Adverse Events by Preterred Term	SAF	×
Class and Preferred Term	SAF	
14.3.1.5 Serious Treatment Emergent Adverse Events by System Organ		
Class and Preferred Term	SAF	Х
14.3.1.6 Related Treatment Emergent Adverse Events by System Organ Class and Preferred Term	SAF	
14.3.1.7 Serious related Treatment Emergent Adverse Events by System	0.15	
Organ Class and Preferred Term	SAF	
withdrawal by System Organ Class and Preferred Term	SAF	х
14.3.1.9 Treatment Emergent Adverse Events leading to death by System		
Organ Class and Preferred Term	SAF	
14.3.3.1 Vital signs: Absolute values and changes from baseline	SAF	
14.3.3.2 Vital signs: Number of subjects (%) with abnormal values by visit	SAF	
14.3.3.3 Vital signs: Shift table from baseline versus each post-baseline visit	0.4.5	
	SAF	
14.3.4.1 Hernatology: Absolute values and changes from baseline	SAF	
14.3.4.2 Hematology: Number of subjects (%) with abnormal values by visit	SAF	

Template Ref: STL-BIS03-00-01 SAP Template v 6.0 effective 11-Mar-2021 This template is an appendix to SOP-BIS03 SAP Filing instructions: File original in TMF section 11.01.01

Protocol title: A RANDOMIZED, VEHICLE-CONTROLLED, SAFETY AND EFFICACY STUDY OF EVO101 IN ADULT SUBJECTS WITH ATOPIC DERMATITIS

Sponsor code: EVO101-AD001

code: EPQ1001

Version number: Final 1.0

Date: 17-AUG-2023

14.3.4.3 Hematology: Shift table from baseline versus each post-baseline visit	SAF	
14.3.4.4 Chemistry: Absolute values and changes from baseline	SAF	
14.3.4.5 Chemistry: Number of subjects (%) with abnormal values by visit	SAF	
14.3.4.6 Chemistry: Shift table from baseline versus each post-baseline visit of Normal/Abnormal values	SAF	
14.3.4.7 Urinalysis: Absolute values and changes from baseline	SAF	
14.3.4.8 Urinalysis: Number of subjects (%) with abnormal values by visit	SAF	
14.3.4.9 Urinalysis: Shift table from baseline versus each post-baseline visit of Normal/Abnormal values	SAF	
14.3.5.1 ECG: Absolute values and changes from baseline	SAF	
14.3.5.2 ECG: Number of subjects (%) with abnormal values by visit	SAF	
14.3.5.3 ECG: Shift table from baseline versus each post-baseline visit of Normal/Abnormal values	SAF	
14.3.6.1 Physical examination: Number of subjects (%) with abnormal values by visit	SAF	
14.3.6.2 Physical examination: Shift table from baseline versus each post- baseline visit of Normal/Abnormal values	SAF	
14.3.7.1 Exposure and compliance data	SAF	Х

9.2 Listings of Individual Subject Data and Other Information to be Produced for the Clinical Study Report

		Key/Top
Title	Population	Results
16.1.7 Randomization Scheme	RND	Х
16.2.1.1 Study discontinuation and reasons for withdrawal	ITT	Х
16.2.1.2 Screening failures including reasons for failure	All	
16.2.2 Protocol deviations	ITT	
16.2.3 Patient disposition in analysis data sets and primary reasons for		Х
withdrawal	ITT	
16.2.4.1 Demographic data	ITT	Х
16.2.4.2 Medical/Surgical history	ITT	
16.2.4.3 Prior medication and therapy	SAF	
16.2.4.4 Concomitant medication and therapy	SAF	
16.2.5.1 Extent of study drug administration compliance	SAF	Х
16.2.6.1 EASI by visit	ITT	Х
16.2.6.2 IGA by visit	ITT	X

Template Ref: STL-BIS03-00-01 SAP Template v 6.0 effective 11-Mar-2021 This template is an appendix to SOP-BIS03 SAP Filing instructions: File original in TMF section 11.01.01

Protocol title: A RANDOMIZED, VEHICLE-CONTROLLED, SAFETY AND EFFICACY STUDY OF EVO101 IN ADULT SUBJECTS WITH ATOPIC DERMATITIS

Sponsor code: EVO101-AD001

code: EPQ1001

Version number: Final 1.0

Date: 17-AUG-2023

16.2.6.3 BSA by visit	ITT	Х
16.2.6.4 Pruritus-NRS by visit	ITT	Х
16.2.6.5 Pharmacokinetic: Plasma levels of EVO101 by visit	PK	
16.2.7.1 Adverse events	SAF	Х
16.2.7.2 Serious adverse events	SAF	
16.2.7.3 Deaths	SAF	
16.2.7.4 Local skin reactions	SAF	
16.2.8.1 Hematology	SAF	
16.2.8.2 Clinical Chemistry	SAF	
16.2.8.3 Urinalysis	SAF	
16.2.8.4 Covid-19 and Pregnancy tests by visit	SAF	
16.2.9 Vital Signs	SAF	
16.2.10 ECG values and interpretation	SAF	
16.2.11 Physical Examination by Body System	SAF	

Protocol title: A RANDOMIZED, VEHICLE-CONTROLLED, SAFETY AND EFFICACY STUDY OF EVO101 IN ADULT SUBJECTS WITH ATOPIC DERMATITIS

Sponsor code: EVO101-AD001

code: EPQ1001

Version number: Final 1.0

Date: 17-AUG-2023

10 Appendices

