15.6. Other Safety Data

Laboratory test results will be summarized descriptively at baseline and Week 8. Additionally, shifts from baseline to Week 8 in laboratory test results based on normal ranges will be summarized with descriptive statistics. Individual laboratory test results will be presented in a by-subject listing. Any clinically significant laboratory abnormalities will be captured as AEs.

Vital signs will be presented by treatment group as observed values and changes from baseline using descriptive statistics.

Medical histories will be coded using the MedDRA dictionary and presented in a by-subject listing.

Concomitant medications will be coded using the WHO-Drug dictionary. Concomitant medications will be summarized by treatment, drug class and preferred term.

Physical examination data will be presented in a by-subject listing.

Descriptive statistics by treatment group and visit will be provided for the following ECG parameters: heart rate (HR), RR duration, QRS duration, PR duration, QT duration and QTcF and QTcB duration.

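### The laboratory shift categories named in the SAP carry no direction, so a fall below range and a rise above it share a cell; shift numeric tests on Low / Normal / High instead (minor).

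*SAP*

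**What the plan says.** - **Protocol 15.6 (Other Safety Data)** plans that "shifts from baseline to Week 8 in laboratory test results based on normal ranges will be summarized with descriptive statistics". It does not name the categories.
- **SAP 8.3.10 (Clinical Laboratory Measurements)** covers hematology, chemistry and urinalysis together. It plans summaries of values and changes from baseline, and by-visit counts in three classes: normal; abnormal but not clinically significant; abnormal and clinically significant. It then plans "A shift table presenting the number and the percentage of subjects in each bivariate category (baseline versus each post-baseline visit"), without listing the categories to be crossed. By-subject listings give the value, the change and a normal/abnormal flag.
- **SAP 9.1 (table list)** has "14.3.4.6 Chemistry: Shift table from baseline versus each post-baseline visit of Normal/Abnormal values" and "14.3.4.9 Urinalysis: Shift table from baseline versus each post-baseline visit of Normal/Abnormal values". The hematology entry reads "14.3.4.3 Hematology: Shift table from baseline versus each post-baseline visit" and, as extracted, names no categories; the line may have been cut.
- **SAP 9.1** also lists by-visit counts, for example "14.3.4.5 Chemistry: Number of subjects (%) with abnormal values by visit", with matching tables for hematology (14.3.4.2) and urinalysis (14.3.4.8).
- **Denominator.** The opening of SAP 8.3.10 bases percentages on available data "except for the shift table for which percentages will be based on the total number of subjects in each treatment arm". SAP 8.3.2 shows subjects without data under a Missing category.

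**The concern.** A reference range has two limits, and crossing one is a different finding from crossing the other. The categories that the SAP names record only whether a value is outside the range and whether the investigator thought it mattered. A count that drops below range and one that climbs above it look the same in the shift table.

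This matters because safety is part of the primary objective and scheduled laboratory tests occur only at Screening and Week 8. The SAP introduction also describes the drug as an inhibitor of a mediator of innate inflammation, so low and high white-cell counts would be read as different signals. If the drug moves an analyte one way, pooling adds background from the other tail to both arms and blurs the contrast that a shift table should show.

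**Working it through.** The plan states no figure on this point, so the check is mainly one of category logic. A numerical illustration under assumptions follows.

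**Step 1. Where each transition falls**

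| Baseline to Week 8 | Normal/Abnormal | Three SAP 8.3.10 classes | Low/Normal/High |
|---|---|---|---|
| Normal to low | normal to abnormal | normal to abnormal (either grade) | normal to low |
| Normal to high | normal to abnormal | normal to abnormal (either grade) | normal to high |
| Low to high | on the diagonal | on the diagonal unless the significance rating changes | low to high |

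The first two rows differ only in the last column. For chemistry and urinalysis, the Normal/Abnormal reading comes from the titles of 14.3.4.6 and 14.3.4.9. For hematology it rests on SAP 8.3.10, where the three classes are the only ones named for any panel.

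**Step 2. Does another display fill the gap?**
- Values and changes (14.3.4.1, 14.3.4.4, 14.3.4.7): direction is kept, but subjects crossing a limit are not counted.
- By-visit abnormal counts (14.3.4.2, 14.3.4.5, 14.3.4.8): categorical and by arm, but not split by direction.
- Listings: direction is kept for each subject, with no summary by arm.
- Adverse event tables: by arm, but protocol 15.6 sends only clinically significant abnormalities there.

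None of these counts, by arm, the subjects who cross a given limit without a clinically significant rating.

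**Step 3. Illustration (assumptions, not document figures)**

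Assume one analyte is normally distributed, its range covers the central 95%, and the active arm falls by *s* standard deviations while vehicle does not move. These are Week 8 prevalences, not baseline-to-Week 8 transitions.

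P(low) = Φ(−1.96 + s); P(high) = Φ(−1.96 − s); pooled = the sum.

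| s | Low | High | Pooled | Low ratio to vehicle | Pooled ratio to vehicle |
|---|---|---|---|---|---|
| 0 (vehicle) | 2.5% | 2.5% | 5.0% | – | – |
| 0.25 | 4.36% | 1.36% | 5.72% | 4.36/2.5 = 1.7 | 5.72/5.0 = 1.14 |
| 0.5 | 7.21% | 0.69% | 7.91% | 7.21/2.5 = 2.9 | 7.91/5.0 = 1.6 |

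With 59 per arm (protocol 15.8), the 0.5 SD case gives 59 × 0.0721 = 4.3 against 59 × 0.025 = 1.5 low results, an excess of 2.8. Pooled, it gives 59 × 0.0791 = 4.7 against 59 × 0.05 = 3.0 abnormal results, an excess of 1.7.

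**Step 4. Denominator**

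Assume 10 of 59 subjects in an arm lack a Week 8 sample and five shift. The all-subjects percentage is 5/59 = 8.5%; among subjects with both values it is 5/49 = 10.2%.

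**The case against.** Most of the case on the other side stands, and it limits the point.

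- **Other categorical displays exist.** A reader might infer that the shift tables are the only categorical laboratory comparison. They are not: the by-visit abnormal counts and the adverse event tables are categorical and by arm. A clinically significant result is preferably recorded as a diagnosis (protocol 13.1.4), which will often imply direction.
- **Direction is not lost from the report.** A uniform 0.5 SD fall is what a mean-change table shows best: with 59 per arm it is 0.5/√(2/59) = 2.7 standard errors on Week 8 values alone. The shift table earns its place when a few subjects cross a limit and the mean barely moves.
- **No conflict with the protocol is proven.** A reader might infer an undeclared departure from protocol 15.6. A normal/abnormal split can rest on normal ranges, the protocol does not name low and high, and the list of changes in SAP 8.1 is absent from the released text.
- **Missing subjects are not hidden.** A reader might infer that a subject without a Week 8 sample is counted as unshifted. SAP 8.3.2 puts such subjects under Missing, so the all-subjects denominator lowers the percentage without misclassifying anyone.
- **Low-to-high is rare.** If both visits were independent, about 0.025 × 0.025 × 59 = 0.04 subjects per analyte per arm would make that change, and fewer with positive within-subject correlation. The practical issue is normal-to-low against normal-to-high.
- **The clinical-significance classes are useful.** Exclusion criterion 9 removes clinically significant chemistry and hematology results at Screening, so a Week 8 result in that class is mostly new. That is a reason to keep the rating.

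**Conclusion.** The point holds as a minor improvement to a descriptive safety display in a phase 2a trial. Under the categories that the SAP names, falls and rises share a cell, and no categorical laboratory summary specified in the released text separates them. What is missing is a by-arm count of subjects crossing each limit when the investigator does not rate the result clinically significant.

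The size is modest. In the illustration, the excess over vehicle is 2.8 subjects for the low category and 1.7 for pooled abnormal, with ratios of 2.9 and 1.6. This rests on assumed normality, a central-95% range and a 0.5 SD effect, none of which comes from the documents. A reader might infer lost power for a safety comparison, but laboratory data are summarised descriptively and no between-arm laboratory test is planned.

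The evidence is firmest for chemistry. For urinalysis, direction matters mainly for pH and specific gravity. For hematology, where direction matters most, it rests on SAP 8.3.10 and not on the title of 14.3.4.3.

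**What to change.** - In SAP 8.3.10, state the shift categories. For numeric hematology and chemistry tests, use Low / Normal / High from the laboratory normal ranges on which protocol 15.6 already relies. Align Tables 14.3.4.3 and 14.3.4.6, and apply the same to pH and specific gravity only in 14.3.4.9; other urinalysis items can stay Normal/Abnormal.
- Keep the investigator's clinical-significance rating in the separate by-visit tables (14.3.4.2, 14.3.4.5, 14.3.4.8).
- Optionally, beside the all-subjects percentage and its Missing category, show the percentage among subjects with both a baseline and a Week 8 value.

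The cost is SAP wording, some reprogramming and slightly larger tables. No new data are needed.
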